Leukemia	Clinical characteristic	Medical record	Yes, No

PFIZER CONFIDENTIAL

Variable	Role	Data source (s)	Operational definition
Malignant lymphoma	Clinical characteristic	Medical record	Yes, No
Peptic ulcer disease	Clinical characteristic	Medical record	Yes, No
Metastatic solid tumor	Clinical characteristic	Medical record	Yes, No
History of ischemic or hemorrhagic stroke	Clinical characteristic	Medical record	Yes, No
History of TIA	Clinical characteristic	Medical record	Yes, No
History of de tromboembolismo	Clinical characteristic	Medical record	Yes, No
Enfermedad coronaria	Clinical characteristic	Medical record	Yes, No
History of de hemorragia gastrointestinal	Clinical characteristic	Medical record	Yes, No
History of Intracranial bleeding	Clinical characteristic	Medical record	Yes, No
History of Other bleeding	Clinical characteristic	Medical record	Yes, No
Bleeding history or predisposition at start OAC treatment	Clinical characteristic	Medical record	Yes, No
INR > 60% at start OAC treatment	Clinical characteristic	Medical record	Yes, No
Use of aspirin at start OAC treatment	Clinical characteristic	Medical record	Yes, No
Use of clopidogrel at start OAC treatment	Clinical characteristic	Medical record	Yes, No
Use of NSAIDs at start OAC treatment	Clinical characteristic	Medical record	Yes, No
HASBLED at start OAC treatment	Clinical characteristic	Medical record	Score – number higher than 0
CHA2DS2-VASc at start OAC treatment	Clinical characteristic	Medical record	Score – number higher than 0
Anaemia at start OAC treatment	Clinical characteristic	Medical record	Yes, No
Stroke	Clinical outcome	Medical record	Yes, No
Time to stroke	Clinical outcome	Medical record	Date of event dd/mm/yy

Pfizer Confidential

Variable	Role	Data source (s)	Operational definition
Type of stroke	Clinical outcome	Medical record	Ischemic stroke, Haemorrhagic or not specified
Pulmonary embolism	Clinical outcome	Medical record	Yes, No
Time to pulmonary embolism	Clinical outcome	Medical record	Date of event dd/mm/yy
Gastrointestinal bleeding	Clinical outcome	Medical record	Yes, No
Time to gastrointestinal bleeding	Clinical outcome	Medical record	Date of event dd/mm/yy
Intracranial bleeding	Clinical outcome	Medical record	Yes, No
Time to Intracranial bleeding	Clinical outcome	Medical record	Date of event dd/mm/yy
Other major bleeding	Clinical outcome	Medical record	Yes, No
Time to other major bleeding	Clinical outcome	Medical record	Date of event dd/mm/yy
CCI			

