ICD-10	Description
N032	Diffuse membranous glomerulonephritis
N033	Diffuse mesangial proliferative glomerulonephritis
N034	Diffuse endocapillary proliferative glomerulonephritis
N035	Diffuse mesangiocapillary glomerulonephritis
N036	Dense deposit disease
N037	Diffuse crescentic glomerulonephritis
N052	Diffuse membranous glomerulonephritis
N053	Diffuse mesangial proliferative glomerulonephritis
N054	Diffuse endocapillary proliferative glomerulonephritis
N055	Diffuse mesangiocapillary glomerulonephritis
N056	Dense deposit disease
N057	Diffuse crescentic glomerulonephritis
N18	Chronic renal failure
N19	Unspecified renal failure
N250	Renal osteodystrophy
Z490	Preparatory care for dialysis
Z492	Other dialysis
Z940	Kidney transplant status
Z992	Dependence on renal dialysis

A: B18, I85, I86.4, I98.2, K70, K71.1, K71.3, K71.4, K71.5, K71.7, K72.1, K72.9, K73, K74, K76.0, K76.2, K76.3, K76.4, K76.5, K76.6, K76.7, K76.8, K76.9, Z94.4

Score 1 point

ICD-10	Description
B18	Chronic viral hepatitis
I85	Oesophageal varices
I864	Gastric varices
I982	Oesophageal varices in diseases classified elsewhere
K70	Alcoholic liver disease
K711	Toxic liver disease with hepatic necrosis
K713	Toxic liver disease with chronic persistent hepatitis
K714	Toxic liver disease with chronic lobular hepatitis
K715	Toxic liver disease with chronic active hepatitis
K717	Toxic liver disease with fibrosis and cirrhosis of liver
K721	Chronic hepatic failure
K729	Hepatic failure, unspecified
K73	Chronic hepatitis, not elsewhere classified
K74	Fibrosis and cirrhosis of liver
K760	Fatty (change of) liver, not elsewhere classified
K762	Central haemorrhagic necrosis of liver
K763	Infarction of liver
K764	Peliosis hepatis
K765	Hepatic veno-occlusive disease
K766	Portal hypertension
Z944	Liver transplant status

S: I64, I69.3, D62, D68.3, D69.8, D69.9, H31.3, H35.6, H43.1, H45.0, H92.2, I23.0, I31.2

Score 1 point

PFIZER CONFIDENTIAL

ICD-10	Description
I64	Stroke, not specified as haemorrhage or infarction
I693	Sequelae of cerebral infarction
D62	Acute posthaemorrhagic anaemia
D683	Haemorrhagic disorder due to circulating anticoagulants
D698	Other specified haemorrhagic conditions
D699	Haemorrhagic condition, unspecified
H313	Choroidal haemorrhage and rupture
H356	Retinal haemorrhage
H431	Vitreous haemorrhage
H450	Vitreous haemorrhage in diseases classified elsewhere
H922	Otorrhagia
I230	Haemopericardium as current complication following acute myocardial infarction

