I312	Haemopericardium, not elsewhere classified

B: I60, I61, I62, I85.0, I98.3, J94.2, K22.6, K25.0, K25.2, K25.4, K25.6, K26.0, K26.2, K26.4, K26.6, K27.0, K27.2, K27.4, K27.6, K28.0, K28.2, K28.4, K28.6, K29.0, K62.5, K66.1, K76.2, K92.0, K92.1, K92.2

Score 1 point

ICD-10	Description
I60	Subarachnoid haemorrhage
I61	Intracerebral haemorrhage
I62	Other nontraumatic intracranial haemorrhage
I850	Oesophageal varices with bleeding
I983	Oesophageal varices with bleeding, , not elsewhere classified
J942	Haemothorax
K226	Gastro-oesophageal laceration-haemorrhage syndrome
K250	Acute with haemorrhage
K252	Acute with both haemorrhage and perforation
K254	Chronic or unspecified with haemorrhage
K256	Chronic or unspecified with both haemorrhage and perforation
K260	Acute with haemorrhage
K262	Acute with both haemorrhage and perforation
K264	Chronic or unspecified with haemorrhage
K266	Chronic or unspecified with both haemorrhage and perforation
K270	Acute with haemorrhage
K272	Acute with both haemorrhage and perforation
K274	Chronic or unspecified with haemorrhage
K276	Chronic or unspecified with both haemorrhage and perforation
K280	Acute with haemorrhage
K282	Acute with both haemorrhage and perforation
K284	Chronic or unspecified with haemorrhage
K286	Chronic or unspecified with both haemorrhage and perforation
K290	Acute haemorrhagic gastritis
K625	Haemorrhage of anus and rectum
K661	Haemoperitoneum
K762	Central haemorrhagic necrosis of liver
K920	Haematemesis
K921	Melaena
K922	Gastro-intestinal haemorrhage, unspecified

L: INR

Score 1 point

E: Elderly \geq 65 years

Score 1 point

D: E24.4, F10, G31.2, G62.1, G72.1, I42.6, K29.2, K85.2, K86.0, T51, Y90.4, Y90.5, Y90.6, Y90.7, Y90.8, Y91.2, Y91.3, Z50.2, Z71.4, Z72.1

1 or 2 point each

ICD-10	Description
E244	Alcohol-induced pseudo-Cushing's syndrome
F10	Mental and behavioural disorders due to use of alcohol
G312	Degeneration of nervous system due to alcohol
G621	Alcoholic polyneuropathy
G721	Alcoholic myopathy
I426	Alcoholic cardiomyopathy
K292	Alcoholic gastritis
K852	Alcohol-induced acute pancreatitis
K860	Alcohol-induced chronic pancreatitis
T51	Toxic effect of alcohol
Y904	Blood alcohol level of 80-99 mg/100 ml
Y905	Blood alcohol level of 100-119 mg/100 ml
Y906	Blood alcohol level of 120-199 mg/100 ml
Y907	Blood alcohol level of 200-239 mg/100 ml
Y908	Blood alcohol level of 240 mg/100 ml or more
Y912	Severe alcohol intoxication
Y913	Very severe alcohol intoxication
Z502	Alcohol rehabilitation

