Bleeding (gastrointestinal, intracranial, other)	I60 Subarachnoid haemorrhage I61 Intracerebral haemorrhage I62 Other nontraumatic intracranial haemorrhage S064 Epidural haemorrhage S065 Traumatic subdural haemorrhage S066 Traumatic subarachnoid haemorrhage I850 Oesophageal varices with bleeding K250 Acute with haemorrhage K252 Acute with both haemorrhage and perforation K254 Chronic or unspecified with haemorrhage K256 Chronic or unspecified with both haemorrhage and perforation K260 Acute with haemorrhage K262 Acute with both haemorrhage and perforation K264 Chronic or unspecified with haemorrhage K266 Chronic or unspecified with both haemorrhage and perforation K270 Acute with haemorrhage K272 Acute with both haemorrhage and perforation K274 Chronic or unspecified with haemorrhage K276 Chronic or unspecified with both haemorrhage and perforation K280 Acute with haemorrhage K282 Acute with both haemorrhage and perforation K284 Chronic or unspecified with haemorrhage K286 Chronic or unspecified with both haemorrhage and perforation K290 Acute haemorrhagic gastritis K625 Haemorrhage of anus and rectum K920 Haematemesis K921 Melaena K922 Gastro-intestinal haemorrhage, unspecified D62 Acute posthaemorrhagic anaemia H356 Retinal haemorrhage H431 Vitreous haemorrhage H450 Vitreous haemorrhage in diseases classified elsewhere H922 Otorrhagia

PFIZER CONFIDENTIAL

Variable	Operacional definition ICD-10
	I312 Haemopericardium, not elsewhere classified J942 Haemothorax R04 Haemorrhage from respiratory passages K661 Haemoperitoneum M250 Haemarthrosis N02 Recurrent and persistent haematuria N938 Other specified abnormal uterine and vaginal bleeding N939 Abnormal uterine and vaginal bleeding, unspecified N950 Postmenopausal bleeding R31 Unspecified haematuria R58 Haemorrhage, not elsewhere classified T792 Traumatic secondary and recurrent haemorrhage
Systemic embolism	I74 Arterial embolism and thrombosis
Alcohol consumption	E244 Alcohol-induced pseudo-Cushing's syndrome E52 Niacin deficiency [pellagra] G312 Degeneration of nervous system due to alcohol G621 Alcoholic polyneuropathy G721 Alcoholic myopathy I426 Alcoholic cardiomyopathy K292 Alcoholic gastritis K70 Alcoholic liver disease K860 Alcohol-induced chronic pancreatitis O354 Maternal care for (suspected) damage to foetus from alcohol T51 Toxic effect of alcohol Z714 Alcohol abuse counselling and surveillance Z721 Alcohol use

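### HAS-BLED item B omits 18 of the 45 codes that Table 2 counts as baseline bleeding: 12 score under no letter and six score under stroke, while K76.2 scores twice

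*Combined protocol and SAP*

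**What the plan says.** Four places in the protocol bear on this point.

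- **HAS-BLED item B (section 7.3.1).** One point is given for any code in a list that starts "B: I60, I61, I62, I85.0, I98.3, J94.2, K22.6, K25.0, K25.2, K25.4, K25.6" and ends "K29.0, K62.5, K66.1, K76.2, K92.0, K92.1, K92.2". The list has 30 codes. K76.2 is among them, labelled "Central haemorrhagic necrosis of liver".
- **HAS-BLED items A (liver) and S (section 7.3.1).** The liver list ends "K73, K74, K76.0, K76.2, K76.3, K76.4, K76.5, K76.6, K76.7, K76.8, K76.9, Z94.4", so it also contains K76.2. The stroke item is "S: I64, I69.3, D62, D68.3, D69.8, D69.9, H31.3, H35.6, H43.1, H45.0, H92.2, I23.0, I31.2", which mixes two stroke codes with haemorrhage codes. Each item is worth 1 point.
- **Table 2, bleeding row (section 7.3.1).** Baseline bleeding (gastrointestinal, intracranial, other) is defined by 45 codes. Among them are "S064 Epidural haemorrhage S065 Traumatic subdural haemorrhage S066 Traumatic subarachnoid haemorrhage" and "R31 Unspecified haematuria R58 Haemorrhage, not elsewhere classified T792 Traumatic secondary and recurrent haemorrhage".
- **Table 1 (section 7.3).** A separate Yes/No field taken from the medical record is called "Bleeding history or predisposition at start OAC treatment". Table 1 also gives the medical record as the source of the HAS-BLED score itself.

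The introduction to the score in section 7.3.1 says it serves to analyse bleeding risk, calls it modified, and says codes are used for each component where they apply.

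**The concern.** Item B is meant to identify patients who have bled before. Table 2 is the protocol's own definition of baseline bleeding. Both are baseline variables, and both feed the first primary objective, which is to describe clinical characteristics. If they disagree, one report can show a patient as having a bleeding history in one row and as having none in the bleeding-risk score.

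The omitted codes are not ones the protocol treats as trivial elsewhere. Its major-bleeding outcome list (section 7.3.1) contains every code in the Table 2 bleeding row. A traumatic subdural haemorrhage after the index date is therefore a major bleed, while the same code before the index date gives no bleeding-history point.

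There is also a problem of reproducibility. The protocol has two possible inputs for item B, the chart field and the code list, and does not say which decides. Two analysts could score the same patient differently.

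**Working it through.** No sample-size or event figure is involved. The check is a comparison of the printed code lists.

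**Inputs, all from section 7.3.1:** item B, 30 codes; Table 2 bleeding row, 45 codes; item S, 13 codes; item A (liver); major-bleeding outcome list, 48 codes (the 45 in Table 2 plus I69.0, I69.1 and I69.2).

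**Step 1. Table 2 bleeding against item B.**
- In both: 27 codes. In Table 2 but not in B: 45 − 27 = 18 (40%).
- In B but not in Table 2: 30 − 27 = 3 (I98.3, K22.6, K76.2).

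**Step 2. Where the 18 go.**
- Under S: D62, H35.6, H43.1, H45.0, H92.2 and I31.2, which is 6.
- Under no HAS-BLED letter: S06.4, S06.5, S06.6, R04, M25.0, N02, N93.8, N93.9, N95.0, R31, R58 and T79.2, which is 18 − 6 = 12. As a share of Table 2, 12/45 = 27%.
- Check: 27 + 6 + 12 = 45.

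**Step 3. Codes in both B and liver.** K76.2 is the only code printed identically in both. In addition, the liver list has the whole category I85 while B has I85.0, so bleeding varices can also score under both.

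**Step 4. Points from A (liver), B and S, using the codes alone.**

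| Only prior code(s) | Table 2 bleeding | As written | Six codes moved from S to B, 12 added to B, K76.2 out of B |
|---|---|---|---|
| S06.5 | Yes | 0 | 1 |
| D62 | Yes | 1 (S) | 1 (B) |
| K92.2 and D62 | Yes | 2 (B + S) | 1 (B) |
| K76.2 | No | 2 (A + B) | 1 (A) |

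If the six codes were added to B but also left in S, a patient with D62 alone would rise from 1 point to 2. They have to be moved, not copied.

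**Step 5. Size of the repaired list.** Table 2 and item B together hold 45 + 3 = 48 codes. Without K76.2 that is 47.

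**Step 6. Patients affected.** The documents give no frequency for any of these codes. If the chart field decides item B and is complete, the number under-scored could be zero. As a conversion only, each 1% of the 7,500 patients (section 7.5) whose sole prior bleeding code is one of the 12 would be 0.01 × 7,500 = 75 patients scored 1 point low.

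**The case against.** The strongest reply is that HAS-BLED need not be scored from codes alone. Table 1 gives the medical record as its source, lists other HAS-BLED inputs (aspirin, clopidogrel and NSAID use, INR, alcohol intake) as chart fields, and has a bleeding-history field that matches how section 5 spells out the item. Section 7.3.1 applies codes only where they are applicable. If the chart field is an input, a charted subdural haemorrhage scores 1. This stands to the extent that a reader cannot claim the field is unused: no section says so. Nor does any section say that it is used, and a 30-code list is printed for B, whereas none is printed for the INR and age items.

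A second reply is that a modified score may use a narrower list than a broad baseline row that includes unspecified haematuria and postmenopausal bleeding. That is fair for some of the 12 codes, but no reason for narrowing is given. It is hard to see one for S06.4 to S06.6 when I60 to I62 are kept.

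A reader might also infer that prior bleeders in general score 0, or that non-gastrointestinal bleeds are missed as a class. The lists do not support either. Of the 45 codes, 27 score under B and six more under S. B itself contains intracranial, pleural and peritoneal bleeds (I60 to I62, J94.2, K66.1), and retinal, vitreous, ear and pericardial bleeds score through S. K76.2 works the other way, by adding a point.

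Finally, section 7.7 rules out treatment comparison, so no adjusted contrast depends on the score. That limits the consequence but does not remove it, because the score describes the population under a primary objective.

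**Conclusion.** The point holds in this form. By the printed lists, item B omits 18 of the 45 codes that Table 2 defines as baseline bleeding. For six the point is kept but credited to stroke, which can also give 2 points for bleeding alone when a B code is present. For 12 (27% of the codes) the bleed earns nothing in the score, although all 12 count as major bleeding after index. K76.2 earns 2 points where one liver condition is recorded.

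The 27% is a share of codes, not of patients. The number of patients mis-scored cannot be derived, because code frequencies are not given and the role of the chart field is not stated. The conclusion on individual scores assumes that the codes decide item B. The conclusion that the rule is ambiguous needs no such assumption. The matter should be corrected before scoring. It affects a descriptive baseline variable, not a treatment contrast.

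**What to change.** In section 7.3.1:

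1. Define item B by the Table 2 bleeding row plus I98.3 and K22.6 (47 codes). At minimum, add S06.4, S06.5 and S06.6 and give the reason for leaving out any of the other nine.
2. Move D62, H35.6, H43.1, H45.0, H92.2 and I31.2 from S to B and delete them from S.
3. Delete K76.2 from B and keep it under liver only. At the same time, state whether I85.0 is meant to score under both B and liver.
4. State that item B is met if the Table 1 bleeding-history field is Yes or if any listed code is recorded before the index date.

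The cost is two revised code lines (B and S) and one or two sentences. The chart field is already planned for collection, so no extra abstraction is needed. The downside is that patients whose only prior bleed was minor will score slightly higher. If that is not wanted, the narrower list in step 1, with its reasons written down, is the alternative, and step 4 must then say how the chart field treats those bleeds.

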7.3.1. Definition of outcome variables

- **OAC escalation:** The dose escalation of the OAC dose will be considered as a dose frequency according to the index dose, as well as the follow-up doses. The proportion of patients experiencing "dose increase", "dose decrease" or "no change" during follow-up with respect to the index dose will be measured, and the time to dose increase or decrease will be calculated.

C
C
I

C
C
I

- **Switch of treatment:** A switch among anticoagulants will be defined as a prescription filled for non-index anticoagulants within +/- 30 days after the date of discontinuation.
- **Persistence:** Persistence will be defined as the time under OAC therapy, calculated as the time in days from the index date to the date of discontinuation or change to treatment. As previously stated, discontinuation will be defined as a change of treatment, that is, to another OAC, or when there is no evidence of a prescription for 60 days from the last supply delivered, whichever comes first.

Therefore, if a patient does not receive his next prescription for the OAC therapy within 60 days after the end of the previous prescription, it will be considered that he discontinued therapy, and the date of the last prescription will be considered as the final date of persistence.

Persistence with OAC therapy will be considered during the period of individual patient follow-up. Patients will be censored at the end of their follow-up period.

- **Major bleeding:** Patients presenting any of the following diagnoses during the follow-up period:

ICD-10	Description
I60	Subarachnoid haemorrhage
I61	Intracerebral haemorrhage
I62	Other nontraumatic intracranial haemorrhage
I690	Sequelae of subarachnoid haemorrhage
I691	Sequelae of intracerebral haemorrhage
I692	Sequelae of other nontraumatic intracranial haemorrhage
S064	Epidural haemorrhage
S065	Traumatic subdural haemorrhage
S066	Traumatic subarachnoid haemorrhage
I850	Oesophageal varices with bleeding
K250	Acute with haemorrhage

Apixaban

B0661148- NON-INTERVENTIONAL STUDY PROTOCOL

Final, 10 October 2019

ICD-10	Description
K252	Acute with both haemorrhage and perforation
K254	Chronic or unspecified with haemorrhage
K256	Chronic or unspecified with both haemorrhage and perforation
K260	Acute with haemorrhage
K262	Acute with both haemorrhage and perforation
K264	Chronic or unspecified with haemorrhage
K266	Chronic or unspecified with both haemorrhage and perforation
K270	Acute with haemorrhage

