I130	Hypertensive heart and renal disease with (congestive) heart failure
I132	Hypertensive heart and renal disease with both (congestive) heart failure and renal failure
I110	Hypertensive heart disease with (congestive) heart failure

- *Peripheral vascular disease*

ICD-10	Description
I70	Atherosclerosis
I71	Aortic aneurysm and dissection
I731	Thromboangiitis obliterans [Buerger]
I738	Other specified peripheral vascular diseases
I739	Peripheral vascular disease, unspecified

PFIZER CONFIDENTIAL

ICD-10	Description
I771	Stricture of artery
I790	Aneurysm of aorta in diseases classified elsewhere
I792	Peripheral angiopathy in diseases classified elsewhere
K551	Chronic vascular disorders of intestine
K558	Other vascular disorders of intestine
K559	Vascular disorder of intestine, unspecified
Z958	Presence of other cardiac and vascular implants and grafts
Z959	Presence of cardiac and vascular implant and graft, unspecified

▪ *Dementia*

ICD-10	Description
F00	Dementia in Alzheimer's disease
F01	Vascular dementia
F02	Dementia in other diseases classified elsewhere
F03	Unspecified dementia
G30	Alzheimer's disease
F051	Delirium superimposed on dementia
G311	Senile degeneration of brain, not elsewhere classified

▪ *Cerebrovascular disease*

ICD-10	Description
G45	Transient cerebral ischaemic attacks and related syndromes
G46	Vascular syndromes of brain in cerebrovascular diseases
I60	Subarachnoid haemorrhage
I61	Intracerebral haemorrhage
I62	Other nontraumatic intracranial haemorrhage
I63	Cerebral infarction
I64	Stroke, not specified as haemorrhage or infarction
I65	Occlusion and stenosis of precerebral arteries, not resulting in cerebral infarction
I66	Occlusion and stenosis of cerebral arteries, not resulting in cerebral infarction
I67	Other cerebrovascular diseases
I68	Cerebrovascular disorders in diseases classified elsewhere
I69	Sequelae of cerebrovascular disease
H340	Transient retinal artery occlusion

▪ *Chronic pulmonary disease*

ICD-10	Description
J40	Bronchitis, not specified as acute or chronic
J41	Simple and mucopurulent chronic bronchitis
J42	Unspecified chronic bronchitis
J43	Emphysema
J44	Other chronic obstructive pulmonary disease
J45	Asthma
J46	Status asthmaticus
J47	Bronchiectasis
J60	Coalworker's pneumoconiosis
J61	Pneumoconiosis due to asbestos and other mineral fibres
J62	Pneumoconiosis due to dust containing silica

PFIZER CONFIDENTIAL

ICD-10	Description
J63	Pneumoconiosis due to other inorganic dusts
J64	Unspecified pneumoconiosis

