Z714	Alcohol abuse counselling and surveillance
Z721	Alcohol use

Codes Anatomical Therapeutic Chemical (ATC): B01AC, M01A

- SMAe-TT₂R₂ score:** The estimation of SAMe-TT₂R₂ will be performed by adding the following variables:

Sex (female) Score 1 point

Age (<60 years) Score 1 point

Medical history (history of more than two of the following: hypertension, diabetes, coronary artery disease or myocardial infarctions, peripheral artery disease, heart failure, stroke; pulmonary, hepatic, or renal disease) Score 1 point

Treatment (interacting medications , amiodarone ATC- C01BD01) Score 1 point

Tobacco use (within 2 years) Score 2 points

PFIZER CONFIDENTIAL

Race (non-Caucasian) Score 2 points

Table 2. Baseline variables or possible confounders

Variable	Operacional definition ICD-10
Diabetes	E10 Insulin-dependent diabetes mellitus E11 Non-insulin-dependent diabetes mellitus E12 Malnutrition-related diabetes mellitus E13 Other specified diabetes mellitus E14 Unspecified diabetes mellitus
Hypertension	I10 Essential (primary) hypertension I11 Hypertensive heart disease I12 Hypertensive renal disease I13 Hypertensive heart and renal disease I15 Secondary hypertension
Ischaemic stroke	I63 Cerebral infarction Excepto I636 Cerebral infarction due to cerebral venous thrombosis, nonpyogenic I64 Stroke, not specified as haemorrhage or infarctionz
Haemorrhagic stroke	I60 Subarachnoid haemorrhage I61 Intracerebral haemorrhage I62 Other nontraumatic intracranial haemorrhage

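### Table 2 leaves the I69 sequelae codes out of its baseline stroke and intracranial-bleed definitions, although Charlson, HAS-BLED item S and the major bleeding outcome use them

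*Combined protocol and SAP*

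**What the plan says.** Table 2 (Section 7.3.1, under the covariate definitions) gives ICD-10 operational definitions for the baseline variables. Three rows matter here:

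- Ischaemic stroke: I63 except I63.6, and "I64 Stroke, not specified as haemorrhage or infarctionz".
- Haemorrhagic stroke: "I60 Subarachnoid haemorrhage I61 Intracerebral haemorrhage I62 Other nontraumatic intracranial haemorrhage".
- Bleeding, whose intracranial part and the code after it read "I62 Other nontraumatic intracranial haemorrhage S064 Epidural haemorrhage S065 Traumatic subdural haemorrhage S066 Traumatic subarachnoid haemorrhage I850 Oesophageal varices with bleeding".

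Other lists in Section 7.3.1 do use I69. The Charlson cerebrovascular item takes the whole category, "Sequelae of cerebrovascular disease". HAS-BLED item S takes I69.3, "Sequelae of cerebral infarction". The major bleeding outcome list takes I690, "Sequelae of subarachnoid haemorrhage", together with I691 and I692.

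Table 1 (Section 7.3) separately lists "History of ischemic or hemorrhagic stroke", and likewise history of intracranial bleeding and of other bleeding. Each is a yes/no field taken from the medical record, with no code list. Section 7.4.2 names the medical record as the source of baseline clinical characteristics, and Section 7.6.1 has trained physicians abstract it.

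**The concern.** A baseline variable for stroke or intracranial bleeding should pick up events that happened before the index date. By its label, a sequelae code belongs to a patient whose event is already past. The protocol accepts that reasoning in Charlson and in HAS-BLED item S. It also applies it inside Table 2, where the myocardial infarction row includes I252 for an old infarction. The stroke rows and the intracranial part of the bleeding row have no counterpart.

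Two things are at stake. First, prior stroke and prior bleeding are clinical characteristics under the first primary objective (Section 6), and a list that misses past events understates them. Second, I690-I692 count as major bleeding when recorded in follow-up but do not count as bleeding at baseline. An old bleed could then enter the Kaplan-Meier analysis of Section 7.7 as a new event. It would also end that patient's follow-up, because Section 7.1 stops follow-up at a major bleed.

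**Working it through.** The plan states no figure on this point, so the check is a comparison of code lists.

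| List | Used for | I69 codes |
|---|---|---|
| Table 2, Ischaemic stroke | baseline | none |
| Table 2, Haemorrhagic stroke | baseline | none |
| Table 2, Bleeding (45 codes) | baseline | none |
| Major bleeding (48 codes) | follow-up outcome | I690, I691, I692 |
| Charlson, cerebrovascular disease | baseline score | I69 (all) |
| HAS-BLED S | baseline score | I69.3 |
| HAS-BLED B | baseline score | none |
| CHA2DS2-VASc S2 | baseline score | none (G45 codes only) |

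**Bleeding row against outcome list.** The two lists differ by 48 - 45 = 3 codes, which are exactly I690, I691 and I692. No code in the Table 2 row is missing from the outcome list.

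**Two patients, classified by codes alone.**

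- Only I69.3 before index: Charlson cerebrovascular disease yes (1 point); HAS-BLED S yes (1 point); Table 2 ischaemic stroke no.
- Only I69.1 before index: Charlson cerebrovascular disease yes (1 point); Table 2 haemorrhagic stroke no; Table 2 bleeding no; HAS-BLED B no. If I69.1 is recorded again during follow-up, the major bleeding outcome is met.

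The same record therefore gives conflicting answers within one baseline table, and conflicting answers between baseline and follow-up.

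**Size, as illustration only.** The documents give neither the prevalence of prior stroke (p) nor the share of those patients who carry only an I69 code (f). With N = 7,500 from Section 7.5, the number missed is N × p × f and the reported prevalence is p × (1 - f). All values of p and f below are assumed.

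- p = 5%, f = 5%: 7,500 × 0.05 × 0.05 = 18.75, about 19 patients; reported prevalence 0.05 × 0.95 = 4.75%.
- p = 10%, f = 20%: 7,500 × 0.10 × 0.20 = 150 patients; reported 0.10 × 0.80 = 8%.
- p = 20%, f = 40%: 7,500 × 0.20 × 0.40 = 600 patients; reported 0.20 × 0.60 = 12%.

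These figures also assume that codes alone decide status and that chart review recovers nobody. The span from 19 to 600 shows only that the effect could be trivial or material.

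**The case against.** The strongest reply is that the variables actually labelled as history are in Table 1. They come from physician abstraction of the medical record, and Section 9 says that the study involves human review of unstructured text. A physician reading a chart can record an old stroke whatever its code. No sentence makes the Table 2 codes decide the Table 1 fields. This stands, and it makes the consequence conditional. It does not remove the problem. Section 7.6.1 requires the variables to be set according to the protocol, Table 2 holds the ICD-10 definitions labelled as baseline, and nothing says that chart text overrides them. The remark on unstructured data in Section 9 concerns adverse-event reporting.

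A reader might infer several stronger points that the documents do not support:

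- *That sequelae-only patients will certainly be tabulated without a history.* This holds only where Table 2 codes decide, which the protocol leaves open.
- *That Table 2 is the lone exception.* HAS-BLED B and CHA2DS2-VASc S2 also omit I69, so the use of these codes is mixed across the protocol.
- *That the bleeding row holds nothing but acute-event codes.* It includes ulcer haemorrhage codes labelled chronic or unspecified (such as K254) and N02 for recurrent haematuria. The gap is in the intracranial part.
- *That the SAMe-TT2R2 history item loses stroke.* That score has no code list for stroke and does not refer to Table 2.
- *That named subgroup results are contaminated.* Section 7.7 does not prespecify a subgroup by prior stroke or prior bleed, and it rules out comparison of treatments.

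**Conclusion.** The inconsistency is confirmed from the protocol's own lists. The three Table 2 rows contain no I69 code, three other lists do, and Table 2 includes a past-event code for myocardial infarction. To the extent that Table 2 codes determine baseline status, patients coded only I69.x are recorded as having no prior stroke or intracranial bleed, and a characteristic in the first primary objective is understated. An old intracranial bleed can also be missed at baseline and then counted as a new major bleed.

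The number affected cannot be computed from the documents. It depends on the prevalence of prior events, on the share coded only as sequelae, and on how many of these the chart abstraction recovers. The point is worth correcting before data extraction because the correction costs little. It is not evidence that the baseline tables will be wrong by any stated amount.

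**What to change.** 1. For baseline history only, add I69.3 and the I69 subcode that corresponds to I64 to the Ischaemic stroke row of Table 2. Add I69.0, I69.1 and I69.2 to the Haemorrhagic stroke and Bleeding rows.
2. Apply the same history codes in HAS-BLED B and CHA2DS2-VASc S2, or state why those items differ.
3. State that the Table 1 history fields are positive if either these codes or the chart review shows a past event.
4. Acknowledge that I690-I692 already sit in the major bleeding outcome list, and reconcile this. Either remove them from the outcome, or count them only where the record dates the bleed after the index date. Step 1 alone does not solve this, because it makes the Table 2 bleeding row identical to the outcome list (45 + 3 = 48 codes) and leaves the outcome rule untouched.

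The cost is a few codes and two or three sentences in the protocol, carried into the data dictionary and abstraction instructions. No new data source is needed. If the outcome codes are kept under a dating rule, abstractors must check the date of the bleed for those records.
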